5.3.2.2 Monitoring and Prophylactic Treatment for Hepatitis B Reactivation

Table 5-3 provides details of monitoring and prophylactic therapy according to the baseline results of viral load and serologic markers testing.

Table 5-3

Action to be Taken for Positive Baseline Hepatitis B Results

Test	Result	Result	Result	Result	Result
HBV-DNA	+	+ or -	-	-	-
HBsAg	+ or -	+	-	-	-
HBsAb	+ or -	+ or -	+ and no prior HBV vaccination	+ or -	or + with prior HBV vaccination
HBcAb	+ or -	+ or -	+ or -	+	-
Recommendation	Prophylaxis treatment should be started 1-2 weeks prior to first dose of study drug Monitor HBV-DNA approximately every 4-8 weeks		No prophylaxis Monitor HBV-DNA approximately every 3-4 weeks		No specific action

Antiviral prophylaxis therapy should continue for at least 4 weeks after last dose of study drug.

For hepatitis B reactivation, definition and management guidelines see Table 5-4 Guidelines for Management of Hepatitis B.

Table 5-4**Guidelines for Management of Hepatitis B**

HBV Reactivation (with or without clinical signs and symptoms)*	

For patients with baseline results:
 
Positive HBV-DNA
 
OR
 
Positive HBsAg
 <hr/> 
Reactivation is defined as:
 
Increase of 1 log in HBV-DNA relative to baseline HBV-DNA value OR new appearance of measurable HBV-DNA
	
Treat: Start a second antiviral
 
AND
 
Interrupt study drug administration until resolution: \leq baseline HBV-DNA levels
 
If resolution occurs within \leq 21 days, study drug should be restarted at one dose lower, if available. If the patient is already receiving the lowest dose of study drug according to the protocol, the patient should restart at the same dose after resolution. Both antiviral therapies should continue at least 4 weeks after last dose of study drug.
 
If resolution occurs >21 days, patients should discontinue study drug but continue both antiviral therapies at least 4 weeks after last dose of study drug.


For patients with baseline results:
 
Negative HBV-DNA and HBsAg
 
AND
 
Positive HBsAb (with no prior history of vaccination against HBV), OR positive HBcAb
 <hr/> 
Reactivation is defined as:
 
New appearance of measurable HBV-DNA
	
Treat: Start first antiviral medication
 
AND
 
Interrupt study drug administration until resolution: \leq baseline HBV-DNA levels
 
If resolution occurs within \leq 21 days, study drug should be restarted at one dose lower, if available. If the patient is already receiving the lowest dose of study drug according to the protocol, the patient should restart at the same dose after resolution. Antiviral therapy should continue at least 4 weeks after last dose of study drug.
 
If resolution occurs >21 days, patients should discontinue study drug but continue antiviral therapy at least 4 weeks after last dose of study drug.

* All reactivations of hepatitis B are to be recorded as grade 3 (CTEP CTCAE Version 4.0 Metabolic Laboratory/Other: Viral Reactivation), unless considered life threatening by the investigator; in which case they should be recorded as grade 4 (CTEP CTCAE Version 4.0 Metabolic Laboratory/Other: Viral Reactivation).

5.3.2.3 Monitoring for Hepatitis C Flare

The following two categories of patients should be monitored every 4-8 weeks for HCV reactivation:

- Patients with detectable HCV RNA-PCR test at baseline.

- Patients known to have a history of HCV infection, despite a negative viral load test at baseline (including those that were treated and are considered 'cured').

For definition of hepatitis C flare and the management guidelines, see Table 5-5 Guidelines for Management of Hepatitis C.

Table 5-5

Guidelines for Management of Hepatitis C

HCV Flare*	

For patients with baseline results:
 
Detectable HCV-RNA:
 
HCV Flare is defined as:
 
$>2 \log_{10}$ IU/mL increase in HCV-RNA
 
AND
 
ALT elevation $>5x$ ULN or 3x baseline level, whichever is higher
	Discontinue study drug.

For patients with baseline results:
 
Knowledge of past hepatitis C infection with no detectable HCV-RNA:
 
HCV Flare is defined as:
 
New appearance of detectable HCV-RNA
 
AND
 
ALT elevation $>5x$ ULN or 3x baseline level, whichever is higher
	Discontinue study drug.

* All flares of hepatitis C are to be recorded as grade 3 (CTEP CTCAE Version 4.0. Metabolic Laboratory/Other: Viral Flare), unless considered life threatening by the investigator; in which case they should be recorded as grade 4 (CTEP CTCAE Version 4.0 Metabolic Laboratory/Other: Viral Flare).

5.3.2.4 Management of Skin Toxicity

For patients with grade 1 toxicity, no specific supportive care is usually needed or indicated. Rash must be reported as an AE. Patients with grade 2 or higher toxicity may be treated with the following suggested supportive measures at the discretion of the investigator: oral minocycline, topical tetracycline, topical clindamycin, topical silver sulfadiazine, diphenhydramine, oral prednisolone (short course), topical corticosteroids, or pimecrolimus.

5.3.2.5 Management of Stomatitis/Oral Mucositis/Mouth Ulcers

Patients with a clinical history of stomatitis/mucositis/mouth ulcers and those with gastrointestinal morbidity associated with mouth/dental infections, irritation of esophageal mucosa e.g. gastroesophageal reflux disease (GERD) and pre-existing stomatitis/mucositis must be monitored even more closely. Patients should be instructed to report the first onset of buccal mucosa irritation/reddening to their study physician immediately.

Suggested prophylactic treatment for prevention of stomatitis/mucositis:

- a) Use 15 mL baking soda/salt mouth rinse QID (swish and spit). Mix 1/3 teaspoon baking soda and 1/3 teaspoon of salt in 1 quart of water (refrigeration is not needed); do not eat or drink anything for 10 minutes after rinsing.
- b) Use 10 mL prescribed “miracle mouth wash” QID (swish and spit). For 16-ounce recipe: 320 mL Benadryl solution, 2 g tetracycline powder, 80 mg hydrocortisone, and 40 mL nystatin suspension, quantity sufficient with water. Wait 10-15 minutes after the baking soda/salt rinse before using “miracle mouthwash”.⁵⁵

Stomatitis/oral mucositis/mouth ulcers due to everolimus should be treated using local supportive care. Please note that investigators in earlier trials have described the oral toxicities associated with everolimus as mouth ulcers, rather than mucositis or stomatitis. If your examination reveals mouth ulcers rather than a more general inflammation of the mouth, please classify the adverse event as such. Please follow the paradigm below for treatment of stomatitis/oral mucositis/mouth ulcers:

1. For mild toxicity (Grade 1), use conservative measures as noted above, baking soda/salt mouth rinse and “miracle mouth wash”.
2. For more severe toxicity (Grade 2 in which case patients have pain but are able to maintain adequate oral alimentation, or Grade 3 in which case patients cannot maintain adequate oral alimentation), the suggested treatments are:

In addition to baking soda/salt mouth rinse and “miracle mouth wash” above, topical analgesic mouth treatments (e.g., local anesthetics such as benzocaine, butyl aminobenzoate, tetracaine hydrochloride, menthol, or phenol) with or without topical corticosteroids, such as triamcinolone oral paste 0.1% (Kenalog in Orabase[®]) or Periogard[®] oral rinse.
3. Agents containing hydrogen peroxide, iodine, and thyme derivatives may tend to worsen mouth ulcers. It is preferable to avoid these agents. Alcohol-containing rinses and tooth paste with sodium lauryl sulfate should also be avoided. Avoid acidic, spicy, hard, or crunchy foods, and consume foods that are tepid rather than hot.⁵⁵
4. Antifungal agents must be avoided unless a fungal infection is diagnosed. In particular, systemic imidazole antifungal agents (ketoconazole, fluconazole, itraconazole, etc.) should be avoided in all patients due to their strong inhibition of everolimus metabolism, thereby leading to higher everolimus exposures. Therefore, topical antifungal agents are preferred if an infection is diagnosed. Similarly, antiviral agents such as acyclovir should be avoided unless a viral infection is diagnosed.

Note: Stomatitis/oral mucositis should be appropriately graded using the functional grading given on the CTEP CTCAE Version 4.0.

5.3.2.6 *Management of Diarrhea*

Appearance of grade 1-2 diarrhea attributed to study drug toxicity may be treated with supportive care such as loperamide, initiated at the earliest onset (for example 4 mg orally followed by 2 mg orally every 2 hours until resolution of diarrhea).

5.3.2.7 *Management of Hyperlipidemia and Hyperglycemia*

Treatment of hyperlipidemia should take into account the pre-treatment status and dietary habits. Grade 2 or higher hypercholesterolemia (>300 mg/dL or 7.75 mmol/L) or grade 2 hypertriglyceridemia or higher (>2.5 times upper normal limit) should be treated with a 3-hydroxy-3-methyl-glutaryl (HMG)-CoA reductase inhibitor (e.g. atorvastatin, pravastatin, fluvastatin) or appropriate triglyceride-lowering medication, in addition to diet.

Note: Concomitant therapy with fibrates and an HMG-CoA reductase inhibitor is associated with an increased risk of a rare but serious skeletal muscle toxicity manifested by rhabdomyolysis, markedly elevated creatine phosphokinase (CPK) levels and myoglobinuria, acute renal failure and sometimes death. The risk versus benefit of using this therapy should be determined for individual patients based on their risk of cardiovascular complications of hyperlipidemia.

Hyperglycemia has been reported in clinical trials. Monitoring of fasting serum glucose is recommended prior to the start of everolimus therapy and periodically thereafter. Optimal glycemic control should be achieved before starting trial therapy.

5.3.2.8 *Management of Non-Infectious Pneumonitis*

Non-infectious pneumonitis is a class effect of rapamycin derivatives. Cases of non-infectious pneumonitis (including interstitial lung disease) have also been described in patients taking everolimus. Some of these have been severe and on rare occasions, a fatal outcome was observed.

A diagnosis of non-infectious pneumonitis should be considered in patients presenting with non-specific respiratory signs and symptoms such as hypoxia, pleural effusion, cough or dyspnea, and in whom infectious, neoplastic and other non-medicinal causes have been excluded by means of appropriate investigations. Patients should be advised to report promptly any new or worsening respiratory symptoms.

Patients who develop radiological changes suggestive of non-infectious pneumonitis and have few or no symptoms may continue everolimus therapy without dose alteration. If symptoms are moderate (Grade 2), consideration should be given to interruption of therapy until symptoms improve. The use of corticosteroids may be indicated. Everolimus may be reintroduced at a reduced dose until recovery to Grade 1 or better.

For cases where symptoms of non-infectious pneumonitis are severe (Grade 3), everolimus therapy should be discontinued and the use of corticosteroids may be indicated until clinical symptoms resolve. Therapy with everolimus may be re-initiated at a reduced dose depending on the individual clinical circumstances.

For non-infectious pneumonitis definition and management guidelines, see Table 5-6 Management of Non-Infectious Pneumonitis.

Table 5-6

Management of Non-Infectious Pneumonitis

Worst Grade Pneumonitis	Required Investigations	Management of Pneumonitis	Everolimus Dose Adjustment
Grade 1	CT scans with lung windows.	No specific therapy is required	No dose adjustment required. Initiate appropriate monitoring.
Grade 2	CT scan with lung windows. Consider pulmonary function testing includes: spirometry, DLCO, and room air O ₂ saturation at rest. Consider a bronchoscopy with biopsy and/or BAL. Monitoring at each visit until return to ≤ grade 1. Return to initial monitoring frequency if no recurrence.	Symptomatic only. Consider corticosteroids and/or other supportive therapy if symptoms are troublesome.	Rule out infection and consider interruption of everolimus until symptoms improve to Grade ≤ 1. Re-initiate everolimus at one dose level lower. Discontinue everolimus if failure to recover within ≤ 21 days.
Grade 3	CT scan with lung windows and pulmonary function testing includes: spirometry, DLCO, and room air O ₂ saturation at rest. Monitoring at each visit until return to ≤ grade 1. Return to initial monitoring frequency if no recurrence. Bronchoscopy with biopsy and/or BAL is recommended.	Consider corticosteroids if infective origin is ruled out. Taper as medically indicated.	Rule out infection and interrupt everolimus until symptoms improve to Grade ≤ 1. Consider re-initiating everolimus at one dose level lower. Discontinue everolimus if failure to recover within ≤ 21 days.
Grade 4	CT scan with lung windows and required pulmonary function testing, if possible, includes: spirometry, DLCO, and room air O ₂ saturation at rest. Monitoring at each visit until return to ≤ grade 1. Return to initial monitoring frequency if no recurrence. Bronchoscopy with biopsy and/or BAL is recommended if possible.	Consider corticosteroids if infective origin is ruled out. Taper as medically indicated.	Rule out infection and discontinue everolimus.

All interruptions or changes to study drug administration must be recorded.

It will be documented whether or not each patient completed the clinical study. If for any patient either study treatment or observations were discontinued the reason will be recorded.

5.3.3 Concomitant Therapies

Patients will be instructed not to take any additional medications (including over-the-counter products) during the course of the study without prior consultation with the local investigator. At each visit, the investigator will ask the patient about any new medications he/she is or has taken after the start of the study drug.

Concomitant medications/significant non-drug therapies taken \leq 28 days prior to start and after start of study drug, including physical therapy and blood transfusions, should be reviewed.

5.3.4 Prohibited Therapies and Restrictions

The following restrictions apply during the entire duration of the study:

- No other investigational therapy should be given to patients.
- No anticancer agents other than the study medication should be given to patients, with the following exceptions:
 - Bisphosphonates, Zometa, or Xgeva for bone metastases
 - a GnRH analog is permitted if the patient had progressive disease on a GnRH analog plus a SERM or an AI; the GnRH analog may continue but the SERM or AI must be discontinued.
- If any other anticancer agents are required for a patient then the patient must first be withdrawn from the study.
- Concurrent radiation therapy is prohibited, however palliative radiotherapy may be considered on a case by case basis after discussion with the Study Chair.
- Patients must not be receiving chronic, systemic treatment with corticosteroids or another immunosuppressive agent greater than or equal to 5 mg prednisone or its equivalent daily. Topical or inhaled corticosteroids are allowed.
- The use of live vaccines and close contact with those who have received live vaccines should be avoided during treatment with everolimus. Examples of live vaccines include intranasal influenza, measles, mumps, rubella, oral polio, BCG, yellow fever, varicella and TY21a typhoid vaccines.
- It is highly recommended that patients with positive HBV-DNA or HBsAg are treated prophylactically with an antiviral for 1-2 weeks prior to receiving study drug (see Table 5-3).
- The antiviral treatment should continue throughout the entire study period and for at least 4 weeks after the last dose of study drug.
- Patients on antiviral prophylaxis treatment or positive HBV antibodies should be tested for HBV-DNA according to study visit schedule.
- Oral contraceptives in preclinical and clinical data have shown everolimus to have CYP3A4 inhibitory activity rather than induction activity, induction of metabolism of contraceptive hormones by everolimus is unlikely. Consequently, administration of everolimus should not reduce the efficacy of oral contraceptives.
- Grapefruit and other citrus juices affect P450 and PgP activity. Concomitant use should be avoided.

5.3.5 Administration of Everolimus and CYP3A4 Inhibitors/Inducers

5.3.5.1 Inhibitors of CYP3A4 and/or PgP

Everolimus is metabolized by CYP3A4 in the liver and to some extent in the intestinal wall.

Therefore, the following are recommended:

Co-administration with strong inhibitors of CYP3A4 (e.g., ketoconazole, itraconazole, ritonavir) or P-glycoprotein (PgP) should be avoided.

Co-administration with moderate CYP3A4 inhibitors (e.g., erythromycin, fluconazole) or PgP inhibitors should be used with caution. If a patient requires co-administration of moderate CYP3A4 inhibitors or PgP inhibitors, reduce the dose of everolimus to 5 mg every other day. Additional dose reductions to every other day may be required to manage toxicities. If the inhibitor is discontinued, the everolimus dose should be returned to the dose used prior to initiation of the moderate CYP3A4/PgP inhibitor after a washout period of 2-3 days.

Grapefruit and other citrus juices affect P450 and PgP activity. Concomitant use should be avoided.

Refer to Appendix C Table 15-0 for list of medications known to induce/inhibit CYP3A4 and Table 15-1 for a list of medications known to inhibit PgP.

5.3.5.2 Inducers of CYP3A4 and/or PgP

Avoid the use of strong CYP3A4 inducers (e.g., phenytoin, carbamazepine, rifampin, rifabutin, phenobarbital, St. John's Wort). If a patient requires co-administration of strong CYP3A4 inducers, an increase in the dose of everolimus up to twice the currently used daily dose should be considered, 5 mg increments. Enzyme induction usually occurs within 7-10 days; therefore everolimus dose should be increased by one increment 7 days after the start of the inducer therapy. If no safety concerns are seen within the next 7 days, the dose can be increased again one additional increment up to a maximum of twice the daily dose used prior to initiation of the strong CYP3A4 inducer. The choice to adjust the dose of everolimus in a patient requiring co-administration of strong CYP3A4 inducers will be done at the discretion of the treating investigator.

This dose adjustment of everolimus is intended to achieve similar AUC to the range observed without inducers. However, there are no clinical data with this dose adjustment in patients receiving strong CYP3A4 inducers. If the strong inducer is discontinued the everolimus dose should be returned to the dose used prior to initiation of the strong CYP3A4/PgP inducer. Refer to Appendix C Table 15-0 for list of medications known to induce CYP3A4 and Table 15-1 for a list of medications known to induce PgP.

Oral anticoagulants such as warfarin are CYP2C9 substrates and, as such, no interaction with everolimus is expected. However, drug-drug interaction studies between macrolide antibiotics and warfarin have produced mixed outcomes and the disparity in these findings has led to the conclusion that multiple factors may alter the

clearance of warfarin. The co-administration of everolimus and oral anticoagulants is possible but should be subject to verification of coagulation (INR) once steady state is reached (after one week's treatment).

A comprehensive list of cytochrome P450 isoenzymes and CYP3A4 inhibitors, inducers, and substrates can be found at:

<http://medicine.iupui.edu/clinpharm/ddis/table.aspx>. This website is continually revised and should be checked frequently for updates.

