Table 15-0

Clinically Relevant Drug Interactions: Inhibitors and Inducers of Isoenzyme CYP3A

INHIBITORS

Strong Inhibitors:
 
clarithromycin, conivaptan, elvitegravir, indinavir, itraconazole, ketoconazole, lopinavir, mibefradil, nefazodone, neflifinavir, posaconazole, ritonavir, saquinavir, telithromycin, tipranavir, troleandomycin, voriconazole
 
(Krishna et al, 2009)
 
Moderate Inhibitors:
 
aprepitant, amprenavir, atazanavir, casopitant, cimetidine, ciprofloxacin, darunavir, diltiazem, dronedarone, erythromycin, fluconazole, fosamprenavir, grapefruit juice (citrus parasidi fruit juice), imatinib, tofisopam, verapamil

INDUCERS

amprenavir, aprepitant, armodafinil (R-modafinil), avasimibe, bosentan, carbamazepine, dexamethasone, efavirenz, etravirine, glucocorticoids, modafinil, naftillin, nevirapine, oxcarbazepine, phenobarbital, phenytoin, pioglitazone, prednisone, rifabutin, rifampin, ritonavir, rufinamide, St. John's wort, talviraline, tipranavir, topiramate, troglitazone

Table 15-1

Clinically Relevant Drug Interactions: Substrates, Inducers, and Inhibitors of PgP and PgP/CYP3A

SUBSTRATES
Colchicines, digoxin, fexofenadine, indinavir, paclitaxel, topotecan, vincristine
INDUCERS
Rifampin, St. John's wort
PgP INHIBITORS and PgP/CYP3A DUAL INHIBITORS
Amiodarone, captopril, carvedilol, clarithromycin, conivaptan, diltiazem, dronedarone, elacridar, erythromycin, felodipine, fexofenadine, ginkgo (ginkgo biloba), indinavir, itraconazole, lopinavir, mibepradil, milk thistle (silybum marianum), nifedipine, nitrendipine, quercetin, quinidine, ranolazine, ritonavir, saquinavir, Schisandra chinensis, St John's wort (hypericum perforatum), talinolol, telmisartan, tipranavir, valspar, verapamil

Reference: Internal Clinical Pharmacology Drug-drug interaction (DDI) memo, updated Oct. 2, 2011, which summarizes DDI data from three sources including the FDA's "Guidance for Industry, Drug Interaction Studies", the University of Washington's Drug Interaction Database, and Indiana University School of Medicine's Drug Interaction Table.

16 Appendix D: New York Heart Association (NYHA) Cardiac Classification of Functional Capacity and Objective Assessment

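### St. John's wort is both a strong inducer in Protocol 5.3.5.2 and a PgP inhibitor in Appendix C, so two rules move the everolimus dose in opposite directions with no rule of precedence

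*Protocol*

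**What the plan says.** Protocol Section 5.3.5.2 opens with "Avoid the use of strong CYP3A4 inducers (e.g., phenytoin, carbamazepine, rifampin, rifabutin, phenobarbital, St. John's Wort" and other such agents. Where one is nonetheless required, "an increase in the dose of everolimus up to twice the currently used daily dose should be considered, 5 mg increments". The increase is stepwise, the second step depends on no safety concern having appeared, and the choice to adjust "will be done at the discretion of the treating investigator".

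Section 5.3.5.1 deals with inhibitors. On the strong ones it says "Co-administration with strong inhibitors of CYP3A4 (e.g., ketoconazole, itraconazole, ritonavir) or P-glycoprotein (PgP) should be avoided". It then says "If a patient requires co-administration of moderate CYP3A4 inhibitors or PgP inhibitors, reduce the dose of everolimus to 5 mg every other day".

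Both sections send the reader to Appendix C to classify a drug. Section 5.3.5.1 says "Refer to Appendix C Table 15-0 for list of medications known to induce/inhibit CYP3A4 and Table 15-1 for a list of medications known to inhibit" (the quote stops just before the word PgP), and Section 5.3.5.2 cites the same two tables for inducers. The lead-in to Appendix C sends inhibitors to 5.3.5.1 and inducers to 5.3.5.2.

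In Table 15-1 the inducer row reads "Rifampin, St. John's wort". The row for PgP and dual PgP/CYP3A inhibitors includes "St John's wort (hypericum perforatum), talinolol".

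**The concern.** The two sections attach opposite actions to two labels, and Appendix C gives both labels to the same product. A site that looks up St. John's wort as instructed reaches one rule that lowers everolimus and another under which raising it is to be considered. Neither section, nor the appendix, says which rule takes precedence.

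What is at stake is mainly the safety of the individual patient. Section 5.3.5.2 itself acknowledges that the upward adjustment has no clinical data behind it, and Table 5-0 defines no dose level above the 10 mg starting dose. Sites would also meet the lists routinely: in Section 7.1 the concomitant-medication check points to Appendix C at pre-study, around Cycle 1 Day 1, on Cycle 1 Day 15, on Day 1 of each later cycle, and at the end of induction or treatment.

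**Working it through.** The plan gives no figure of its own to reproduce here. The check has three parts.

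**1. Which drugs are on both sides of Appendix C.** I compared the inhibitor and inducer lists of Tables 15-0 and 15-1.

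| Drug | Listed as inhibitor | Listed as inducer | Route through 5.3.5.1 | Route through 5.3.5.2 |
|---|---|---|---|---|
| St. John's wort | PgP (15-1) | CYP3A (15-0), PgP (15-1), and named as strong in 5.3.5.2 | Reduce | Avoid; if required, consider an increase |
| Aprepitant, amprenavir | Moderate CYP3A (15-0) | CYP3A, strength not given (15-0) | Reduce | Increase only if read as strong |
| Ritonavir, tipranavir | Strong CYP3A (15-0) and PgP/dual (15-1) | CYP3A, strength not given (15-0) | Avoid as strong CYP3A4 inhibitors; reduce only through the PgP/dual listing | Increase only if read as strong |

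Section 5.3.5.2 gives six examples of strong inducers. St. John's wort is the only one of the six that is also on an inhibitor list.

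**2. How direct each conflict is.** For St. John's wort no assumption is needed: the text calls it a strong inducer and the table calls it a PgP inhibitor. For the other four drugs, the increase can be reached only by treating the Table 15-0 inducer list as a list of strong inducers. Table 15-0 splits inhibitors into strong and moderate but leaves inducers ungraded, although 5.3.5.2 confines the increase to strong ones. A reader therefore cannot settle the matter from the table.

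**3. Size of the gap.** The inputs are the dose levels in Table 5-0 (10 mg daily, 5 mg daily, 5 mg every other day) and the two rules above.

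- Inhibitor rule: 5 mg every other day = 5/2 = 2.5 mg/day on average, whatever the current dose.
- Inducer rule, ceiling: 2 × current daily dose.
- From 10 mg daily: ceiling 2 × 10 = 20 mg/day; 20/2.5 = 8-fold.
- From 5 mg daily: ceiling 2 × 5 = 10 mg/day; 10/2.5 = 4-fold.
- From 5 mg every other day: ceiling 2 × 2.5 = 5 mg/day; 5/2.5 = 2-fold. Here the inhibitor rule changes nothing, because the patient is already at that dose.

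The 20 mg ceiling is reached only after two 5 mg steps (10 + 5 = 15, then 15 + 5 = 20). After the first step the gap is 15/2.5 = 6-fold.

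**The case against.** The strongest reply is that the protocol already contains the problem. Strong inducers and strong inhibitors are to be avoided. Section 5.3.3 tells patients to take no additional medication, over-the-counter products included, without first consulting the investigator. The increase is optional, stepwise and discretionary, and 5.3.5.1 introduces its own rules as recommendations. A drug can also have both properties: Table 15-1 cites an interaction memo built on three sources, so a double listing is not in itself a mistake.

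Most of this stands, and it limits how often the conflict would arise. It does not remove the conflict. Both sections go on to say what to do when the drug is required, and it is those two rules that disagree. The discretion clause covers adjustment for strong inducers only; it does not say whether the reduction for a PgP inhibitor gives way.

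Three stronger readings are tempting, and the documents do not support them.

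- *A reader might infer that all five dual-listed drugs receive opposite instructions.* Only St. John's wort does on the wording. Aprepitant and amprenavir are nowhere called strong inducers, and ritonavir and tipranavir are first of all drugs to avoid.
- *A reader might infer that steroids given for pneumonitis trigger a dose increase*, since prednisone, dexamethasone and glucocorticoids are on the inducer list. They are nowhere called strong inducers, and Section 5.3.2.8 with Table 5-6 gives its own instructions for that event.
- *A reader might infer uncontrolled dose variation across the everolimus arm.* Nothing in the documents suggests that enough patients would be exposed for that.

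**Conclusion.** The point holds as an internal contradiction for one product, St. John's wort, together with a lesser ambiguity for four others that comes from the ungraded inducer list in Table 15-0. The gap between the two rules is at most 8-fold, and that is a worst case: it sets a fixed reduction against the ceiling of an optional increase from the full starting dose.

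The conclusion rests on reading 5.3.5.1 as applying its reduction to any PgP inhibitor in Table 15-1. That section is not fully clear on this, because its sentence on avoidance can be read to cover strong PgP inhibitors too and Table 15-1 does not grade them. On that reading the first advice in both sections is to avoid the drug, and the rules for a required drug still diverge.

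Few patients are likely to be affected. No effect on sample size, power, type I error or the primary PFS analysis is claimed. The point matters because an error in the direction of a dose change bears on patient safety even when it is rare.

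**What to change.** The sponsor should reconcile Sections 5.3.5.1 and 5.3.5.2 with Appendix C so that every dual-listed drug (St. John's wort, aprepitant, amprenavir, ritonavir, tipranavir) leads to a single instruction, either by resolving the listing or by stating which section takes precedence. Table 15-0 should mark which inducers are strong for the purpose of 5.3.5.2, as it already does for inhibitors. How each drug is classified, and any dose rule that follows, is for the sponsor to decide; this review takes no position on either.

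The cost is a short protocol amendment: edits to the Appendix C tables and a cross-reference in each section. Under Section 11.1 a change needs sponsor and IRB approval before sites implement it. No change to data collection or to the analysis is needed.
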